### Visit 2 (3 hours total)

After Visit 1, all participants will complete fMRI and lab procedures, then patients with LW-EDs will be randomized to an intervention.

- (1) fMRI-EMG reversal food-cue learning task and disgust conditioning task (Total completion Time: 2hrs) Both tasks will take place within the scanner. Participants will first be given instructions for the two tasks and will do a short practice version in the mock scanner with the study coordinator to ensure they are comfortable. Participants will be in the fMRI scanner for a total of 1 hour.
- a. Reversal food-cue learning task: During phase one of the Reversal Food Validation fMRI task, (i.e., Acquisition) participants will be presented with visual food or neutral stimuli on a computer screen. Some stimuli, conditioned stimuli, will sometimes be followed by a food or a no outcome (e.g., loss or gain of a food item, M&Ms or Hershey's kisses). Other stimuli will never be followed by an outcome and will be used for comparison. Phase two of the task, Reversal, is similar to Acquisition only the reinforcement contingencies will be reversed. That is, some of the previously non-paired stimuli will be now paired with the outcome while the previously paired stimuli will be now unpaired. A response pad will be placed around the participant's right arm and the participant will be instructed to make ratings. Participants will also have MRI safe EMG electrodes from BioPac systems attached in order to provide a physiological measure of learned contingencies. For this task, participants are instructed that afterwards they will be given the equivalent number of M&Ms (240) or Hershey's kisses (48) that they are presented in the task, regardless of their responses.
- b. **Disgust choice conditioning task**: The conditioning procedure will test the ability to learn and extinguish disgust associations. The task includes distinct acquisition and extinction phases. In the acquisition phase, the conditioned stimuli (CS), consisting of blue and green squares, will be presented individually at fixation, followed 4 s later by the co-presentation of the unconditioned stimuli (UCS) to the left and right of the CS. The UCS will consist of two sets of pictures

depicting either intact fresh food or rotted versions of the same food items. Subjects will be instructed to attend to possible associations between the CS and UCS and to rate the "disgust" versus "desire" associated with the UCS on a Likert scale presented during the inter-trial interval using a 5-button fiber optic system on the right hand. In the extinction phase, the CS will be displayed again individually at fixation, but the UCS will not be presented alongside the CS and the ITI will not include the Likert scale. Subject awareness of the response contingencies will be assessed with a post-scan interview.

(2) **Reversal \$\$-cue learning** (completion time, 25 min): This paradigm mirrors that of the fMRI-EMG except that it is completed outside the scanner with stimuli delivered via laptop and keypad used for item response. The stimuli will be a small monetary rewards that correspond to 15 cent reinforcements as cued by pictures of either 15 pennies or 3 nickels. Participants are instructed that afterwards they will be given the equivalent amount of money that they are presented in the task, either 240 pennies or 48 nickels equating to \$2.40, regardless of their responses.

The stimuli for the food-cue learning task and the \$\$-cue task are paired and counter-balanced for the pre- and post-scans. The 2 stimuli groups include M&Ms/pennies and Hershey's kisses/nickels. Participants randomized to M&Ms/pennies in the pre-scan will receive Hershey's kisses/nickels in the post-scan, and vice versa.

## (3) Lab eating paradigm (Multi-Item Meal)

Along with the fMRI scan, participants will also participate in an eating behavior task as a part of the study. Prior to beginning the study, participants will be instructed to eat all daily meals as usual, with no meal occurring within 4 hours prior to the eating behavior task. Participants will be given scripted instructions by a study coordinator and will be asked to "eat as much or as little as you'd like." They will be presented with a multi-item meal that will consist of a variety of foods (e.g., bread, chicken, apples, oranges, oreos, potato chips, etc.).

As part of the task, participants will also be asked to make ratings before and after the test meal using the VAS. . Participants will be instructed to ring a bell to indicate the end of the meal, and will be asked to complete questionnaires. Test meals will be observed via closed-circuit television by a member of the staff. Outcome measures will include amount consumed, macronutrient distribution, and duration of eating.

Since it is possible participants will be distressed following the multi-item meal, study coordinators will conduct a short debriefing interview with them after completion.

Protocol Title:	Reward Systems and Food Avoidance in Adolescents with
	Low Weight Eating Disorders
Principal Investigator	[name]
Name/Contact Info:	[contact]; [contact]
Primary Contact	[name]
Name/Contact Info	[contact]; [contact]
Date Revised:	
Study Number:	GCO#15-0939 IF# 2446156 HS# 16-00570

### **Treatment (Visits 3-8)**

After the baseline assessment (Visits 1-2), patients with LW-EDs will be randomized to 6 weekly sessions of FBT-WG or IE. Randomization will occur after we have processed the baseline fMRI scans. If the study coordinators have determined the participant's scan is free of interference from motion in the scanner, the participant will be randomized within this group. If the study coordinators determine a participant's scan is unusable, the participant will be excluded from the study.

In both FBT-WG and IE, the first session lasts two hours and the remaining 5 sessions last one hour.

FBT-Weight Gain Control (FBT-WG): Participants and families randomized to FBT-WG will receive 6-weeks of FBT treatment for AN. Sessions occur weekly, with the first session lasting two hours and the remaining 5 sessions one hour. FBT is atheoretical in terms of the etiology, but uses parent-enforced contingencies to increase value of eating and decrease the value of food avoidance. The six sessions of FBT focus primarily on disordered eating, using a functional analysis to facilitate parental use of positive/negative contingencies to motivate eating behavior. In session 2, a family meal provides the therapist with an opportunity for direct observation of the familial interaction patterns around eating. The therapist makes careful and persistent requests for united parental action toward re-feeding and/or regulating eating habits, the primary concern at this point of the treatment, and the therapist tries to create and reinforce a strong parental alliance around efforts at feeding the child, and align the patient with the sibling sub-system. Parents are taught to reinforce even minimal efforts at eating and creating clear consequences for food avoidance and successful eating. Weekly sessions offer an opportunity for therapist to reinforce/update the contingency plan and reinforce the parents for remaining consistent and persistent in their re-feeding of the adolescent.

**IE-Paradigm:** Participants randomized to this intervention are provided with a meal replacement shake of 'unknown' Kcal or macronutrient content and are asked to mindfully observe the sensations (aversive taste, texture, bloating, icky feeling, etc.) and associated emotional states (i.e., disgust) with the empathetic support of parents/therapist in session, without expectation of habituation. The IE 6-session paradigm builds on our proposed model of food avoidance in AN(10), which posits that a conditioned aversive response to food coupled with a pleasurable response to the absence of food accounts for maladaptive food avoidance. Sessions occur on a weekly basis with session one lasting 2 hrs. During the 1st hour, the therapist explains an aversive conditioning model of LW-ED, sensory components of eating, and the concept of IE. The therapist explains the goal of IE is to help patients learn to

Protocol Title:	Reward Systems and Food Avoidance in Adolescents with
	Low Weight Eating Disorders
Principal Investigator	[name]
Name/Contact Info:	[contact]; [contact]
Primary Contact	[name]
Name/Contact Info	[contact]; [contact]
Date Revised:	
Study Number:	GCO#15-0939 IF# 2446156 HS# 16-00570

tolerate their interoceptive experience (e.g., disgust), so that eating can become more flexible. At the end of the first session, the therapist and parent(s) review a manual, which provides clear instructions for structuring the re-feeding process (e.g., sitting with child during all mealtimes; guidelines for IE homework; planning meals). In the 2nd hour, participants are given a meal replacement shake and instructed to focus on internal bodily sensations and to continue eating while experiencing and labeling these sensations. This practice is then assigned for homework, charging parents with orchestrating IE in similar pattern using a visceral sensitivity hierarchy established in the first session and is continued through the end of the module. The therapist uses an empathetic active stance to encourage IE that will subsequently serve as an example for parents in IE homework assignments. Participants rate their level of distress 4 times in the session and physiological response is recorded using EMG and facial recognition software. The remaining 5 sessions last one hour, and participants eat a meal replacement shake over 30-minutes, identical to the first session. All sessions include debriefing and development of IE homework that includes daily practice of IE.

Visit 9 and 10: These visits will follow the same procedures as Visits 1 and 2 respectively.

The eating sessions in visits 1 and 2 and visits 3 and 4 (9 and 10 for adolescents with a low weight eating disorder) and the treatment sessions (visits 3-8) will be video recorded to be decoded via software to analyze participants' emotional responses to eating. Treatment integrity will also be evaluated from the recording of the intervention sessions. The video recordings will be stored securely for the duration of the study in a password protected file that only the study staff can access.

# g) Specimen Banking

Not applicable.

# h) Data Management and Confidentiality

### DATA SHARING PLAN

We will share the primary outcome data from this project with the National Data Archive managed by the National Institutes of Mental Health. The data archive contains anonymized raw data from NIH sponsored programs and research for use in testing reliability of findings from these studies and allowing for future discovery from these data by other investigators or in combination with data collected from other investigators.

Protocol Title:	Reward Systems and Food Avoidance in Adolescents with
	Low Weight Eating Disorders
Principal Investigator	[name]
Name/Contact Info:	[contact]; [contact]
Primary Contact	[name]
Name/Contact Info	[contact]; [contact]
Date Revised:	
Study Number:	GCO#15-0939 IF# 2446156 HS# 16-00570

Our plan will be to upload our primary outcomes which include neuroimaging data (structural scan, BOLD sequence, and task behavioral data) as well as participant weight, eating, and self-report questionnaire data. No identifying information will be shared (e.g., video data, names, address, date of birth). All data will be stored via a unique ID, generated by the data archive that is independent of the unique ID by which data at Mount Sinai is stored. These two IDs will only be stored by the Mount Sinai investigators.

## a) Data Management and Confidentiality

All data stored in the computer database will be anonymized when entered into the database. Data will be stripped of all personal identifiers and each subject will be referred to by a unique research code. The file that contains the link between identifying information and the research code will be kept in a locked file cabinet in the Mount Sinai EWDP in a different location from where the data stored with the research code is maintained. Only authorized members of the research staff will have access to this link.

National Database for Autism Research (NDAR) Data-Sharing -With parental consent, this study will collect and provide research data and related findings to the National Database Archive (NDA). NDA is a biomedical informatics system and data repository created by the National Institutes of Health – part of the U.S. Department of Health and Human Services (DHHS), an agency of the U.S. Government – to assist biomedical researchers working to develop a better understanding of mental health and/or to develop more effective methods to diagnosis, treat and prevent mental health conditions. Data entered into NDA will be kept confidential, with NDA being designed for access by researchers only. Data provided to NDA as part of participation in this research study can not be linked to your identifying information. Once data are uploaded, they will not have a direct link back to identifying information held at Mount Sinai. If parents consent to sharing data with NDA, they mat at any time request that their data or their child's data be removed from NDAR, but they must do so in writing to the Principal Investigator at the address on the first page. If they do not want to consent to sharing their data, they will still be eligible for participation in this study.

b)

Protocol Title:	Reward Systems and Food Avoidance in Adolescents with
	Low Weight Eating Disorders
Principal Investigator	[name]
Name/Contact Info:	[contact]; [contact]
Primary Contact	[name]
Name/Contact Info	[contact]; [contact]
Date Revised:	
Study Number:	GCO#15-0939 IF# 2446156 HS# 16-00570

Raw data will be stored in locked filing cabinets in the project coordinators' office in the EWDP at The Mount Sinai Medical Center. The data to be stored will include deidentified information pertaining to consented participants will receive individualized identifier codes that will be generated in advance of any data acquisition. These codes will be used on all future documents instead of names. An Excel file of the key to the codes (that links names of participants to assigned codes) will be password protected on an encrypted personal network drive that only Mount Sinai EDWP staff can access. Additionally, only designated study staff will have access to the locked password key containing the password to this file. The de-identified data to be stored will include information pertaining to demographic and psychiatric status obtained from the questionnaires and clinical interview. Data will be stored for a minimum of 7 years, with the exception of the video recordings that will only be stored for the duration of the study. All questionnaire and interview data and video recordings will use study identification numbers and electronically stored data will be coded and password protected in a secure database (with a password protected back-up device in a locked office).. Contact information for participants' parents will also be stored on a password protected file and will only be used for scheduling purposes. Only the coordinator and the Principal Investigator will have direct access to this information. The Primary Investigator, [name], will provide intermittent review of procedures employed to ensure proper data management that protects participant confidentiality. The research data file will be kept on an encrypted personal network drive on the Academic Computing file server located in the medical center's secure data center.

# c) Provisions to Monitor the Data to Ensure the Safety of subjects

Only the primary investigator and the research assistants within his laboratory have access to file cabinet keys and computer passwords.

**MSSM Principal Monitor:** Indicate whether this person is the PI, a Team Member, or is Independent:

PI:

Last Name: [name] First Name: [name]

Academic Title: Senior Faculty Member

Department: Psychiatry

Mailing Address: [name]

[contact] [contact]

Protocol Title:	Reward Systems and Food Avoidance in Adolescents with
	Low Weight Eating Disorders
Principal Investigator	[name]
Name/Contact Info:	[contact]; [contact]
Primary Contact	[name]
Name/Contact Info	[contact]; [contact]
Date Revised:	
Study Number:	GCO#15-0939 IF# 2446156 HS# 16-00570

E-mail: [contact]

The research team will have methods in place for dealing with any adverse events that may arise during study procedures. The PI will ensure that any adverse events that occur are recorded and reported within 24 hours of discovery to the ISMMS IRB; this includes both expected and unexpected adverse events.

All prospective participants will also be screened for psychotic symptoms using the KSADs. Any endorsement of psychotic symptoms will exclude the participant from the study; however, referrals will be made for the treatment of these symptoms.

In the case of active suicidal or homicidal plans or intent revealed during the course of evaluation, a licensed psychologist/psychiatrist will evaluate the patient. If necessary, the participant will be taken to the emergency room or admitted to the inpatient facility. In the discovery of a previously unknown psychiatric disorder during evaluation, if safety is compromised or could potentially be compromised, the procedure above will be followed. If not (e.g., the discovery of a Major Depressive Disorder with no psychotic features and no suicidality), the participant will be notified and encouraged to seek help in a sequenced fashion following treatment. The patient's primary clinician will also be notified assuming a written release is signed by the participant.

In the event of a medical emergency during study procedures, emergency services will be notified to take the patient to the hospital.

In the case of clinically significant worsening of eating disordered symptoms identified during study participation, a clinician will determine whether the patient needs to be referred to a higher level of care based on the clinical standards for adolescents utilized within the Eating and Weight Disorders Program. The clinician and PI will subsequently determine whether the patient needs to be withdrawn from the study (e.g., in the case of a referral for psychiatric medication), or if continued participation is possible (e.g., brief medical hospitalization with a new medical clearance to receive outpatient treatment from the treatment team). We will not interfere with any recommendations about the decision to receive or discontinue outpatient treatment made by the providers providing additional care to study participnts.

# d) Withdrawal of Subjects

Patients are free to end their participation in the study at any point. In addition, patients may be discharged involuntarily if they meet any exclusion criteria during the

Effective Date: 4/12/2022 End Date:4/11/2023

Protocol Title:	Reward Systems and Food Avoidance in Adolescents with
Trotocor ritie.	Low Weight Eating Disorders
Principal Investigator	[name]
Name/Contact Info:	[contact]; [contact]
Primary Contact	[name]
Name/Contact Info	[contact]; [contact]
Date Revised:	
Study Number:	GCO#15-0939 IF# 2446156 HS# 16-00570

course of their participation (i.e. if a patient becomes pregnant). If a patient is withdrawn from the study, the research team will explain the reasons for the withdrawal. Withdrawal from this study will not affect a patient's clinical care or access to any care or other opportunities to which they are otherwise entitled. Subjects may also withdraw permission for the use and disclosure of any protected information for research, but must do so in writing to the Principal Investigator at the address listed in the consent document.

Participants with low weight EDs will be informed that not participating in the study will not change or restrict their eligibility for treatment in the Eating and Weight Disorders Program and will not jeopardize their relationship with their pediatric subspecialist, if they were referred from Pediatric Associates or the Adolescent Health Center.

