#### Exclusion criteria:

- Current psychotropic medication that would have an effect on performance on behavioral tasks (i.e., anti-anxiety medication),
- Comorbid psychotic or bipolar disorder,
- Active suicidal ideation,
- Major medical illness known to influence eating or weight,
- Current substance dependence,
- Previous exposure therapy for LW-ED.
- Physical limitation that would prevent participation (e.g., allergic to chocolate),
- For patients with current or a history of sexual or physical abuse by parents, siblings, or guardians, perpetrators of the abuse will be excluded from treatment; if physical or sexual abuse by a family member occurs during the course of treatment, perpetrators will be excluded from ongoing treatment

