## d) Study Timelines

Participants' participation will include 10 visits over approximately 8-week period for AN participants and 4 visits for healthy comparison controls. During the 6 weeks separating the testing, adolescents with low weight EDs will receive an intervention (please see below), whereas healthy comparison adolescents will not have additional contact with study staff during this time.

Visit 1 will consist of screening procedures to determine eligibility, completion of self-report questionnaires, and a laboratory based eating measure.

In Visit 2, all participants will complete a reversal learning computerized task while undergoing an fMRI scan with EMG, computerized task also using EMG, and lastly the completion of a multi-item meal task in which we will analyze eating behavior via video recording and facial recognition software.

The next 6 visits will only apply for **LW-ED participants and not healthy controls** and will consist of the exposure-based intervention, across a span of 6 weeks. Participants will be randomized into one of two intervention groups, a weight gain control group and an interoceptive exposure group.

In Visit 9, all participants will complete self-report measures, single item meal task, and height and weight.

Protocol Title:	Reward Systems and Food Avoidance in Adolescents with	
	Low Weight Eating Disorders	
Principal Investigator	[name]	
Name/Contact Info:	[contact]; [contact]	
Primary Contact	[name]	
Name/Contact Info	[contact]; [contact]	
Date Revised:		
Study Number:	GCO#15-0939 IF# 2446156 HS# 16-00570	

In Visit 10, all participants will complete the same self-report questionnaires, concurrent fMRI--EMG, and computerized learning task, and the multi-item meal task.

After the 10 visits, LW-ED participants are offered 20 sessions of free open-label family-based treatment.

The duration anticipated to enroll all study subjects is 42 months [~1.5 LW-ED patients per month with 60 enrolled by ~month 40 (2 months start-up)], leaving 6 months to analyze the data.

The anticipated duration of the study is 4 years.

The study is estimated to be completed 4 years from the date of initial IRB approval.

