## If found eligible after these assessments, the participant will complete the single-item meal and will be scheduled for Visit 2.

Single-Item Meal: A standardized laboratory test meal will be used as an objective assessment of food avoidance in adolescents with LW-EDs. The meal consists of a strawberry yogurt shake used previously in a study of AN by [name] (Co-I)(30). Limited intake observed in this test meal before and after intensive inpatient treatment and subjective reports of anxiety by patients suggest the utility of this paradigm for LW-EDs. Procedures are based on those described by Sysko et al.(30, 31), and will be identical for experimental IE sessions. Participants will be presented with an 55 fluid ounce (1626.50-mL) covered opaque container containing approximately 1475 grams (1 kcal per gram, or 1475 kcal) of strawberry yogurt shake. Patients will be informed that the meal consists of a strawberry yogurt shake, but will not be told the amount provided in the container. The instructions will direct participants to consume as much of the shake as they would like and that the meal will serve as their lunch (or dinner) for the day and to avoid touching or manipulating the container in any way. The meal will be placed on a modified

Protocol Title:	Reward Systems and Food Avoidance in Adolescents with
Trotocor ritie.	Low Weight Eating Disorders
Principal Investigator	[name]
Name/Contact Info:	[contact]; [contact]
Primary Contact	[name]
Name/Contact Info	[contact]; [contact]
Date Revised:	
Study Number:	GCO#15-0939 IF# 2446156 HS# 16-00570

[figure not shown]
version of an eating monitor, which measures intake (in g) every 5 s. During the meal, participants will also be observed through a closed-circuit video monitor to ensure that they are following instructions and to monitor behavior. Ratings will be made before and after the test meal of hunger, fullness, sickness, loss of control, urge to eat, preoccupation with thoughts of food, disgust, and fear of fatness on a 15-cm visual analog scales (VAS). Consumption of the shake in Kcal will be the primary outcome, with secondary outcomes of rate of eating in Kcal/min during the 30 min meal.

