# 11) Payment to Subjects

All participants will be paid \$275 for the pre and post-intervention assessments. Specifically, participants will be paid \$50 for visit 1, \$65 for visit 2, \$70 for visit 3 (visit 9 for adolescents with eating disorders), and \$90 for visit 4 (visit 10 for adolescents with eating disorders).

**Follow-up Treatment**: LW-ED participants will also be offered 20 free sessions of open label psychotherapy for their eating low weight eating disorderover a maximum of six months in the EWDP as compensation for participation. If participants wish to attend these sessions, the first session will continue approximately one week after

Protocol Title:	Reward Systems and Food Avoidance in Adolescents with
	Low Weight Eating Disorders
Principal Investigator	[name]
Name/Contact Info:	[contact]; [contact]
Primary Contact	[name]
Name/Contact Info	[contact]; [contact]
Date Revised:	
Study Number:	GCO#15-0939 IF# 2446156 HS# 16-00570

Visit 10 and all 20 sessions would be completed within 6-months following Visit 10. When deciding to participate in this study, all participants will be made aware of the full range of treatment option offered by the EWDP, including that our program routinely offers free treatment for eating disorders through our student extern therapists. Therefore, participants should feel no obligation to participate in this study only to receive free treatment for their eating disorder.

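### Randomised patients who worsen or newly meet an exclusion criterion can be withdrawn from the whole study, and nothing keeps their Visit 9 and 10 outcomes

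*Protocol*

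**What the plan says.** Two sections of the protocol govern departure after randomisation.

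- **Section d) Withdrawal of Subjects:** "patients may be discharged involuntarily if they meet any exclusion criteria" while taking part. The same section then describes the consequence as leaving the study: "If a patient is withdrawn from the study, the research team will explain the reasons for the withdrawal".
- **Section c) Provisions to Monitor the Data to Ensure the Safety of subjects:** if eating-disorder symptoms worsen to a clinically significant degree, the clinician and the principal investigator "determine whether the patient needs to be withdrawn from the study (e.g., in the case of a referral for psychiatric medication"). The only alternative given is continued participation, for example after a brief medical hospitalisation.

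The exclusion criteria for low-weight eating disorder (LW-ED) patients include active suicidal ideation and "Current psychotropic medication that would have an effect on performance on behavioral tasks (i.e., anti-anxiety medication").

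The outcomes at stake come after the six treatment sessions. Section d) Study Timelines states: "In Visit 9, all participants will complete self-report measures, single item meal task, and height and weight". The questionnaires, the fMRI-EMG scan, the learning task and the multi-item meal follow at Visit 10. For the single-item meal, "Consumption of the shake in Kcal will be the primary outcome". The data sharing plan counts weight, eating and questionnaire data, as well as neuroimaging, among the study's primary outcomes.

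**The concern.** The protocol knows only two states after randomisation: in the study, or withdrawn from it. It has no state in which the intervention has stopped but assessments continue. A patient withdrawn because she deteriorated, was referred for medication or developed suicidal ideation leaves without post-treatment weight, questionnaires, meal intake or scan. Her missing values are likely to be worse than those of the patients who stay.

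Two results could be affected. Pre-to-post change within each arm would look too favourable. The randomised comparison in Aim 3, and the part of Aim 4 that follows the intervention, would be biased if the two arms lose patients in different numbers or for different reasons. The withdrawal decision is taken with allocation known: the principal investigator shares in it, is also one of the providers of the experimental behavioral challenge (section 4), and is listed as the monitor. The protocol does not show that this leads to imbalance, but nothing in these sections guards against it.

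An analysis plan can choose how to handle missing values. It cannot recover visits that were never made.

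**Working it through.** **Reading the sections together**

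1. Sections c) and d) both describe withdrawal from the study, not from the intervention.
2. Study Timelines and the procedures section schedule Visits 9 and 10 for all participants. Someone withdrawn from the study is no longer a participant, and no section invites her back.
3. Section c) Number of Subjects recruits 118 to obtain complete assessments on 60 + 30 = 90. That leaves room for 118 − 90 = 28 losses, or 28/118 = 23.7%. Losses are met by recruiting more, not by following those lost. The 28 also cover controls, exclusions before randomisation (ineligibility, unusable baseline scan) and voluntary dropout.
4. Weight, questionnaires and shake intake are collected at Visit 9, which has no scan. Possible confounding of the scan by new medication is therefore no reason to lose them.

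**Illustrative size**

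The protocol gives no post-randomisation withdrawal rate, allocation ratio or number randomised per arm. The assumptions are equal arms of 33 to 39 and a latent clinical course correlated r with the outcome, with the worst-placed patients on that course withdrawn. The upper limit of 39 is close to half of 118 × 2/3 ≈ 79, which itself assumes that recruitment follows the 60:30 split.

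*Within one arm.* If the worst fraction f is lost, the observed mean improves by r × φ(z_f)/(1 − f) SD, where z_f is the f-quantile of the standard normal and φ its density. For f = 0.10: φ(−1.282) = 0.1755, and 0.1755/0.90 = 0.195. With r = 0.5 this is 0.097 SD.

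| Fraction lost | r = 0.3 | r = 0.5 | r = 0.7 |
|---|---|---|---|
| 5% | 0.033 | 0.054 | 0.076 |
| 10% | 0.058 | 0.097 | 0.136 |
| 15% | 0.082 | 0.137 | 0.192 |

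*Between arms, no true effect.* Simulation with 40,000 runs per row, two-sample t-test, two-sided 5% level:

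| Lost per arm | r | Bias (SD) | Type I error |
|---|---|---|---|
| 4 v 4 of 35, like reasons | 0.5 | 0.00 | 5.7% |
| 2 v 4 of 33 | 0.5 | 0.05 | 6.0% |
| 2 v 6 of 39 (5% v 15%) | 0.5 | 0.08 | 7.0% |
| 4 v 4 of 35, different kind | 0 v 0.5 | 0.10 | 7.4% |
| 6 v 12 of 39 (15% v 31%) | 0.3 | 0.07 | 6.1% |
| 6 v 12 of 39 (15% v 31%) | 0.7 | 0.16 | 12.3% |

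The formula supports the simulated biases. For 2 v 6 of 39, φ(z_f)/(1 − f) is 0.111 and 0.280, and 0.5 × (0.280 − 0.111) = 0.085 SD. A repeat of the simulation with a fresh random seed agreed to within 0.01 SD and 0.3 percentage points. The first row shows that trimming alone lifts the error rate to 5.7%, so the excess due to arm differences in the next three rows is 0.3 to 1.7 points.

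**The case against.** The strongest reply is that silence is not a rule. Nothing forbids assessing a withdrawn patient, and Visits 9 and 10 are not restricted to those who finish the sessions. The triggers are also narrow. Section c) decides case by case and expressly allows some worsening patients to continue. The only example in section d) is pregnancy, which is not a poor outcome. Most exclusion criteria are unlikely to track response, and the medication criterion covers only drugs that affect task performance. Aim 3 is about neurocircuitry, and new medication can confound a scan. The between-arm biases are small beside the roughly 0.72 SD detectable with 80% power if 30 v 30 complete (two-sided 5%), and an unseen analysis plan could use baseline data and session recordings to handle missing values.

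Much of this stands, and it limits the point. Withdrawal is discretionary, the sizes are modest in most cases, equal and like losses leave the contrast unbiased, and no arm imbalance is shown. The case of 6 v 12 of 39 is an extreme bound: it has nearly all of the assumed 79 LW-ED recruits randomised and makes all 18 losses outcome-driven.

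It does not remove the defect. Worsening is itself the trigger in section c), and a need for medication or new suicidal ideation can plausibly mark a poor course. Scan confounding does not touch the Visit 9 measures. A missing-data method has to assume what an actual weight or meal record would have shown.

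**Conclusion.** The point holds and should be fixed. Followed as written, the protocol can lose post-treatment outcomes for reasons related to how the patient is doing, and no later analysis can restore them. Under the stated assumptions, a 5 to 15% loss improves the within-arm mean by about 0.05 to 0.14 SD at r = 0.5. The between-arm bias runs from nil, when losses are equal and alike, to 0.05–0.10 SD in the moderate cases, with type I error of 6.0 to 7.4%. The bound is 0.16 SD and 12.3%. All of these rest on assumed withdrawal rates, arm sizes and correlations. That withdrawn patients have no provision for Visits 9 and 10 rests on the text alone. Confidence in the practical importance is medium, because the number of such withdrawals is unknown.

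**What to change.** Amend sections c) and d) to distinguish a patient whose study intervention is stopped from one who is withdrawn from the study. Leave all clinical decisions, and who takes them, unchanged. State that a randomised patient who stops the intervention, or later meets an exclusion criterion:

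- is still invited to the existing Visits 9 and 10, unless consent is withdrawn or attendance is unsafe;
- provides at least weight, questionnaires and the meal tests, and the scan where safe, with any new medication recorded;
- stays in her randomised arm.

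In the same amendment, reconcile the pregnancy example in section d) with the LW-ED exclusion list, which does not mention pregnancy.

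The cost is a short amendment and matching consent wording. Each patient retained costs $70 for Visit 9 and $90 for Visit 10 under section 11, so $160, plus staff and scanner time. The drawback is that some scans will be affected by new medication and may need to be flagged.
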